10.2. Specification of the Primary Analysis

The primary endpoint will be change in FVC (in liters) from baseline to 48 weeks. A mixed model repeated measures (MMRM) analysis, will be used to compare differences in the FVC measurements across treatment groups at 48 weeks.²² Response variables are values of the FVC measured at baseline and every 12 weeks until study completion at 48 weeks. Covariates in the model will include treatment time terms and the baseline FVC values. Contrast estimates of differences between treatments (along with confidence intervals) will be used to estimate the treatment effect. The validity of this model in terms of meeting modeling assumptions will be assessed via standard modeling diagnostics and goodness-of-fit measures. The MMRM models will be implemented using PROC MIXED in SAS. For subjects randomized to no surgery who subsequently undergo surgery as part of the study (per protocol), post-surgical FVC measurements will be obtained but will not be included in the assessment of the primary endpoint. Instead, a 48 week FVC value will be imputed based on the pre-surgical FVC values obtained in each individual patient.

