5.4 Study Design and Study Visits

Subjects who appear to meet entry criteria will review the informed consent (a written description of the purpose, procedures, and risks of the study) with the principal investigator (PI), co-investigator, or study coordinator, and all questions will be answered. The informed consent form will be signed by the subject at the beginning of the screening visit. No protocol-specific procedures will be performed until the subject has signed and dated an informed consent form. This includes the screening procedures.

The enrollment visit should occur within 90 days of the screening visit. However, it is preferred that the enrollment visit occur within 28 days of the screening visit to avoid repeating procedures.

All follow-up study visits will occur within 10 business days of their designation (e.g. week 12 will occur +/- 10 business days from the week 12 timepoint).

		Visit							
Study Procedure	Procedure details	Screen V1	Enroll V2	Surgery V2A	Wk 12 V3	Wk 24 V4	Wk 36 V5	Wk 48 V6	Wk 52
Medical history	 Complete medical history 	•							
Physical examination	Physical exam	•			•	•	•	•	
Documentation of GER	 Symptom questionnaire 	٠				•		•	Р
Assessment of esophageal motility and pH	> pH and manometry	•+				•&			H O N
Laparoscopic anti- reflux surgery *				•					Е
Bronchoscopy *				•				•^	V
Spirometry (Hand-held)									I S
Spirometry (Office based)		٠	•#		•!	•!	•!	•!	I T
DLCO			•		•!	•!		•!	
Arterial blood gas		•			•	•		•	
6 minute walk test		•	●#		•	•		•	
HRCT			•@					•	
Patient reported outcomes	 UCSD SOBQ Cough VAS SGRQ ICECAP EQ-5D 		•		•	•	•	•	
Blood collection			•		•	•	•	•	

Table 1. Table of Study Visits

* These procedures will be performed only in those subjects randomized to surgery.

+Does not need to be completed if done within 6 months of V2 at the study site in accordance with the study protocol.

@ Does not need to be completed if done within 3 months of V2 at the study site in accordance with the study protocol.

Only performed if V2 performed > 28 days after V1.

^ This is an optional procedure and will only be performed if the subject has consented for it.

! If a subject has undergone fundoplication surgery (regardless of treatment assignment) within 8 weeks of this visit date, the subject should not undergo this procedure.

& The pH and manometry should be done a minimum of 12 weeks after surgery, and only in those subjects randomized to surgery.

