6.1. Primary Endpoint

The primary endpoint of this study will be the change in FVC (in liters) from baseline to week 48.

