10.1. Sample Size Determination and Randomization

We are planning to enroll approximately 58 subjects randomized in a 1:1 ratio to laparoscopic anti-reflux surgery or standard care. Patients will be allocated using a computer generated randomization scheme. Due to the unblinded nature of the study intervention, the randomization will not be stratified. If enough subjects randomized to surgery are unable to undergo surgery due to failure of insurance authorization or medical eligibility reasons, consideration will be given to rebalancing and/or adjusting randomization to insure sufficient subjects undergo surgery to meet the aims of the study.

In powering the study, we have considered the potential impact of PPI use for symptomatic GER (part of standard medical care) on the rate of FVC change in the no surgery group. Under the assumption that the use of PPIs will be partly effective, our statistical power will be reduced. Based on historical knowledge of change in FVC over time in patients with IPF a difference of 1.0 standard deviation over a one-year period would be approximately 0.25 liters. We believe that a treatment difference of that size would be both clinically meaningful and consistent with our preliminary data. We have conservatively estimated that 40% of individuals in the no surgery group will take PPIs on a regular basis for control of typical GER symptoms (i.e. heartburn and dyspepsia), and that PPIs are 50% as effective as surgery in reducing the rate of decline in FVC over time. With these adjustments, the expected effect size is reduced to 0.8 standard deviations. For that reason, this study is powered to detect an effect size of 0.8 standard deviations (or approximately 0.20 liters) in

the change in FVC between the two groups with a two-sided alpha of 0.05 and 80% power. The estimated number of subjects required for varying effect size and power are shown in Table 3. These calculations are based on the two-sample t-test with an increase in the sample size to allow for up to 10% withdrawal of consent.

Total subjects	Effect size	Two-sided alpha	Power
38	1.0	0.05	80%
52	1.0	0.05	90%
58	0.8	0.05	80%
76	0.8	0.05	90%
100	0.6	0.05	80%
134	0.6	0.05	90%

Table 3: Enrollment requirements for varying effect size and power

*Calculations allow for 10% withdrawal of consent.

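### The primary MMRM uses baseline FVC as both response and covariate: it has no valid fit if the baseline variance is free, and its week-48 standard error is distorted if variance is pooled

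*Combined protocol and SAP*

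**What the plan says.** Section 6.1 sets the endpoint: "The primary endpoint of this study will be the change in FVC (in liters) from baseline to week 48". Section 10.2 describes one model for it, an MMRM in PROC MIXED, which "will be used to compare differences in the FVC measurements across treatment groups at 48 weeks".

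Two consecutive sentences of section 10.2 define that model:
- Response: "Response variables are values of the FVC measured at baseline and every 12 weeks until study completion at 48 weeks".
- Covariates: "Covariates in the model will include treatment time terms and the baseline FVC values".

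The treatment effect is described only in general terms: "Contrast estimates of differences between treatments (along with confidence intervals) will be used to estimate the treatment effect". On model checking, validity "will be assessed via standard modeling diagnostics and goodness-of-fit measures".

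The section does not give a covariance structure, say whether the baseline slope is common or differs by visit, say that the baseline row is dropped or constrained, or name a replacement if the model fails. Section 10.3 applies the MMRM models to the longitudinal secondary endpoints and adds no detail.

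**The concern.** A baseline measurement can be a covariate, with only post-baseline values as responses, or it can be a response that is not also a covariate. Taken literally, section 10.2 does both. At the baseline visit the covariate predicts the response exactly, so the residual is zero or close to it. Such a row tells us nothing about treatment, yet it enters the estimation of the variance.

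This is the only model stated for the primary endpoint. Depending on the covariance structure, it either cannot be fitted, so that an unplanned repair is needed, or it returns an answer whose SE, confidence interval and p-value depend on a row that carries no information.

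**Working it through.** **Inputs from the plan.** Five response rows per subject, and a contrast between arms at week 48 (10.2). SD of change about 0.25 L, effect 0.8 SD, two-sided alpha 0.05, 80% power, 1:1 allocation, 58 subjects, 10% withdrawal (10.1).

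**Assumptions, because the plan is silent.** Covariance structure, correlation, baseline slope, pattern of change SD over visits, baseline SD (0.8 L) and visit-error SD (0.05-0.11 L).

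**1. The plan's own figure.** A two-sample t-test for 0.8 SD needs 26 per arm, or 52 in total. 52/0.9 = 57.8, rounded up to 58. This reproduces section 10.1, and since it rests on a t-test it does not depend on the MMRM.

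**2. Baseline variance free (unstructured or heterogeneous).** Slope 1 makes every baseline residual zero. The log-likelihood then gains n × ln 10 for each tenfold fall in the baseline residual SD, without limit. With n = 52 this is 52 × 2.3026 = 119.7. A numerical check with n = 58 agrees: -2 log L fell from -631 to -764 to -1032 as the baseline variance went from 0.1 to 0.01 to 0.0001, which is 58 × 2.3026 = 133.5 per tenfold step in variance. There is no maximum.

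**3. Pooled variance, compound symmetry (CS), slope 1, complete data.** One row in five has zero residual, so the pooled variance is 4/5 of the post-baseline variance. The SE ratio (with/without the baseline row) is √0.8 = 0.894, or 10.6% lower at any correlation. REML simulation gave 0.893-0.894. With 26 per arm, the SE without the row is 0.25 × √(2/26) = 0.0693 L. The 95% half-width is 2.01 × 0.0693 = 0.139 L, which becomes 0.139 × 0.894 = 0.125 L.

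**4. Pooled variance, AR(1), slope 1, constant change SD.** Large-sample fit:

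| Correlation | SE ratio | SE lower by |
|---|---|---|
| 0.3 | 0.891 | 10.9% |
| 0.6 | 0.877 | 12.3% |
| 0.9 | 0.841 | 15.9% |
| 0.99 | 0.819 | 18.1% |

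**5. Settings with a smaller reduction.** If a common slope is fitted and the true slope is 0.8, the SE is about 7-8% lower under CS and about 9% lower under AR(1). If change SD grows over visits (random slope or random walk), the AR(1) reduction is about 7-11%. An assumed steeper growth, from 0.05 L to 0.25 L, brings it to 5-6%.

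**6. False-positive rate.** If the SE is r times its correct value, the rate is about 2 × [1 - Φ(1.96r)]: 8.0% at r = 0.894 and 10.8% at r = 0.82. In null REML simulations (26 per arm, 4,000 trials per setting, constant change SD) it was 6.7-9.8% with the row and 4.4-5.5% without.

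**7. Missing rows.** Section 10.1 notes: "Calculations allow for 10% withdrawal of consent". The Table 1 footnote on spirometry says that if fundoplication took place "within 8 weeks of this visit date, the subject should not undergo this procedure", so week-12 FVC can be missing in the surgery arm. With m post-baseline rows per subject, the CS ratio is roughly √(m/(m+1)); m = 3.6 gives √(3.6/4.6) = 0.885, or 11.5% lower. A simulation with 29 per arm, 10% random withdrawal and an assumed 20% of the surgery arm without week-12 FVC gave 12% (CS) and 12-14% (AR(1)).

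**8. Where the direction changes.**
- Change SD falling from 0.35 L at week 12 to 0.25 L: SE over true SD is 1.06-1.10 (CS) and 0.99-1.08 (AR(1)), and the false-positive rate is 2.8-4.9%. Falling from 0.30 L: 0.97-1.00 and 0.90-0.97.
- Contrast taken as week 48 minus baseline, under CS with constant SD: the ratio is √[2(0.8 - 0.6ρ)], which is 1.11, 1.00 and 0.72 at ρ = 0.3, 0.5 and 0.9.
- Random intercept and slope: the baseline row raises the SE by 2-9%.
- Sandwich SE: false-positive rate 4.7-6.3%.

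**9. Equal variance as a separate cause.** For a random walk, the change variances at the four visits stand as 1:2:3:4. Pooling them without the baseline row gives √(2.5/4) = 0.79 of the true week-48 SD; with the row it gives √(2/4) = 0.71. The larger part of that error comes from forcing equal variance.

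**10. After the repair.** With baseline as covariate only, the false-positive rate was 4.0-5.7%, checked by week-48 ANCOVA as the complete-data equivalent.

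**The case against.** The double use is plain in the text and I see no charitable reading that removes it. The case on the other side concerns size and direction, and most of it stands.

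- **Nothing in the plan selects pooled variance.** The SE reductions need a pooled structure, model-based SEs, a contrast at week 48 and an analyst who overlooks near-zero residuals at one visit in five. The promised diagnostics ought to show that pattern. This stands, but section 10.2 names no remedy once it is seen.
- **The percentages are not bounds.** A common slope is a natural reading, since no baseline-by-visit term is listed, and it gives smaller reductions if the true slope is below 1. This stands.
- **The direction is not fixed.** Section 6.1 defines the endpoint as a change, and a week-48-minus-baseline contrast can give an SE that is too large. This stands.
- **With growing change SD, pooling is often the larger error.** Without the baseline row, the pooled SE was already 0.72-0.88 of the true SD. This stands.
- **The free-variance failure reveals itself** and could be found on dummy data before database lock. A repair chosen after seeing results is possible, not established.

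A reader might infer that the trial's primary test will have a 7-10% error rate, that the treatment estimate is biased, or that the sample size is wrong. The documents support none of these. The first needs choices the plan does not make, the point estimate is essentially unaffected, and N rests on a t-test.

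**Conclusion.** Wrong as written, and it must be fixed. The firm ground is the contradiction itself and the absence of a valid fit when the baseline variance is free. The SE effect under pooled variance is real but conditional: 10.6% lower under CS with slope 1, about 11-18% under AR(1) with constant change SD, about 7-8% under CS with a common slope truly 0.8, and about 7-11% under AR(1) with that slope or with growing change SD. With constant change SD, this takes a nominal 5% test to roughly 7-10%. The SE may instead be about right or too large under the conditions in step 8.

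These figures rest on the plan's 0.25 L and on the assumptions listed above. They do not cover the imputation of week-48 FVC for control subjects who cross over to surgery, so they do not describe the whole planned analysis. That the problem carries over to the longitudinal secondary endpoints is likely but inferred from section 10.3.

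**What to change.** Give baseline one role in section 10.2.

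- **Preferred.** Responses at weeks 12, 24, 36 and 48 only. Fixed effects: treatment, visit, treatment-by-visit, baseline FVC and baseline-by-visit. Primary contrast: the treatment difference at week 48.
- **Alternative.** Keep baseline as a response with a common mean across arms and drop it as a covariate. Primary contrast: the between-arm difference in change from baseline to week 48. This option was not simulated here.

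In the same edit, state an unstructured covariance and one prespecified fallback for non-convergence. In section 10.3, say that the longitudinal secondary endpoints use the same form.

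The cost is a few sentences, with no new data, visits or subjects. The SE may be slightly larger than the pooled model as written would report.

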5.3. Exclusion Criteria

- 1. FVC < 50% predicted
- 2. FEV1/FVC ratio < 0.65
- 3. Resting room air PaO2 < 60mm Hg
- 4. Unable to walk 50 meters on 6 minute walk test
- 5. Recent acute respiratory illness in last 12 weeks
- 6. Participated in an interventional clinical trial for an IPF therapy in the last 28 days (subjects may be screened, but cannot be enrolled until 28 days after trial participation) [Note: open-label extensions or expanded access programs (EAPs) for pirfenidone or nintedanib are not considered interventional clinical trials and are not exclusionary.]
- 7. Listed for lung transplantation at screening
- 8. Unable to safely undergo full (complete) laparoscopic gastric anti-reflux surgery (i.e. not a partial fundoplication), in the judgment of the investigators
- 9. History of esophageal / bariatric / gastric surgery
- 10. History of cancer (other than non-melanoma skin cancer) in the last 3 years
- 11. Pregnant at the time of screening or enrollment
- 12. Unlikely to obtain pre-authorized approval from a third party payer for laparoscopic anti-reflux surgery and related costs in the opinion of the investigators.
- 13. Life expectancy < 48 weeks due to another illness
- 14. BMI > 35
- 15. Known severe pulmonary hypertension (mean pressure > 35 mm Hg on RHC; RVSP > 50 mm Hg on ECHO)

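### The primary FVC model has no term for baseline pirfenidone or nintedanib use, so it gives up a little precision and leaves a chance imbalance uncorrected

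*Combined protocol and SAP*

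**What the plan says.** Section 5.3, exclusion 6, concerns recent participation in interventional IPF trials. It adds that "open-label extensions or expanded access programs (EAPs) for pirfenidone or nintedanib are not considered interventional clinical trials and are not exclusionary". None of the other 14 exclusions mentions these drugs, so users can be randomized.

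On design, Section 10.1 says "We are planning to enroll approximately 58 subjects randomized in a 1:1 ratio to laparoscopic anti-reflux surgery or standard care", and then: "Due to the unblinded nature of the study intervention, the randomization will not be stratified". The only background treatment that the sizing allows for is PPI use in the control arm.

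Section 10.2 takes FVC at baseline and at weeks 12, 24, 36 and 48 as the response in an MMRM and estimates the treatment contrast at week 48. On adjustment it says: "Covariates in the model will include treatment time terms and the baseline FVC values".

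Sections 10.1 to 10.3 contain no antifibrotic covariate, subgroup or sensitivity analysis, and no rule for antifibrotics started after randomization. Table 1 schedules a complete medical history at screening but has no concomitant-medication row.

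**The concern.** Section 10.1 accepts that background treatment can alter FVC decline: PPI use alone lowers the planned effect from 1.0 to 0.8 SD. Section 10 makes no comparable provision for two drugs that Section 5.3 names in a criterion about IPF therapy.

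With about 26 evaluable subjects per arm, the share of users can differ noticeably between arms by chance. If the drugs affect FVC, the realised surgery contrast then carries part of the drug effect. The trial is unblinded, so a covariate added after an imbalance has been seen would look chosen to suit the result. It carries full weight only if it is prespecified.

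The reason given for not stratifying, that the intervention is unblinded, does not bear on this. A baseline term in the model needs no stratified allocation and reveals nothing about the next assignment.

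**Working it through.** **Inputs from Section 10.1.** The SD comes from "a difference of 1.0 standard deviation over a one-year period would be approximately 0.25 liters". The target is 0.8 SD, or about 0.20 L, with two-sided alpha 0.05 and 80% power by a two-sample t-test, "with an increase in the sample size to allow for up to 10% withdrawal of consent".

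**The plan's own figure.** The effect size is 1.0 × (1 − 0.40 × 0.50) = 0.8. The noncentral t needs 26 per arm (power 80.7%), so 52 evaluable, and 52 / 0.90 = 57.8, which rounds up to 58. The stated size reproduces, as do the other five rows of Table 3.

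**Assumptions (not in the documents).** Share of users p = 0.3 to 0.5. Drug effect on FVC at 48 weeks g = 0.05 to 0.15 L.

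**1. How often is use imbalanced?** The SD of the arm difference is √(2p(1−p)/26):
- p = 0.3: √(0.42/26) = 0.127
- p = 0.5: √(0.50/26) = 0.139

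Twenty points of 26 is 5.2 subjects, so the arms must differ by at least 6 users. Two independent binomials give an exact probability of 9.5% (p = 0.3) to 12.6% (p = 0.5).

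**2. What does it do to the estimate?** Shift = g × imbalance. At 20 points this is 0.05 × 0.20 = 0.010 L to 0.15 × 0.20 = 0.030 L, or 5% to 15% of 0.20 L. The standard error is 0.25 × √(2/26) = 0.069 L, so the shift is 0.14 to 0.43 SE. Given that imbalance, the two-sided rejection rate under no surgery effect is 5.2% to 7.1%. Power for a true 0.20 L falls to 67% to 77% if the imbalance favours control.

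**3. Averaged over randomizations.** In 100,000 simulated trials per scenario (p = 0.5, g = 0.10 and 0.15 L), type I error was 4.9% and the mean estimate was 0.200 L for a true 0.20 L.

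**4. What does adjustment gain?** Explained variance is R² = g²p(1−p)/0.25²:
- Smallest: 0.0025 × 0.21 / 0.0625 = 0.8%
- Largest: 0.0225 × 0.25 / 0.0625 = 9.0%

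With residual SD 0.25 × √(1−R²), power at 26 per arm rises from 80.7% to between 81.1% and 84.3% (81.0% to 84.2% after one degree of freedom is charged). If 0.25 L excludes variation due to these drugs, the unadjusted model has 77.3% to 80.4% power and adjustment restores about 80.7%. Both are single-endpoint approximations, not MMRM calculations.

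**5. Which term is needed?** Take 16 users against 10, with a drug effect rising linearly to 0.15 L at week 48. The unadjusted shift is 0.15 × 6/26 = 0.035 L.
- Baseline FVC in the response, as Section 10.2 states: a term that is constant over time moves every visit equally and cancels from week 48 minus baseline. Generalized least squares leaves the full 0.035 L.
- Response read as post-baseline change only: a constant term corrects in part, by an amount that depends on the covariance. Under compound symmetry it absorbs the mean effect over the four visits, 0.15 × (0.25 + 0.50 + 0.75 + 1.00)/4 = 0.094 L, and leaves (0.150 − 0.094) × 6/26 = 0.013 L. With a random slope and measurement error of SD 0.15 down to 0.05 L, scaled to an SD of change of 0.25 L, it leaves 0.017 to 0.032 L.
- Use-by-visit interaction: the shift is 0.000 L under either reading.

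**The case against.** The strongest reply is that randomization already protects the analysis. The estimate is unbiased, alpha holds, and the confidence interval already reflects chance imbalance in a factor that is not adjusted for. Choosing few covariates with 58 subjects is defensible. No passage says that either drug slows FVC decline, by how much, or how many subjects take it. Section 3 still states that no approved therapy exists, although Section 11.2 gives the arrival of one as an example for the DSMB to consider.

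All of that stands. It limits the point to precision and to the realised trial, and it makes every size above conditional on assumed values. It does not favour omission, because the adjustment is cheap and is credible only if fixed in advance.

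Three stronger readings are tempting, and the documents do not support them:
- A reader might infer that exclusion 6 already puts the covariate in the database. It screens for trial participation, not drug use, so a subject on an ordinary prescription would not be identified by it.
- A reader might infer that surgery and drug effects could not be told apart. A baseline table or a sensitivity analysis would show an imbalance, and nothing in the plan prevents either.
- A reader might infer that one added main effect would suffice at no cost. Step 5 of the working shows that it would not.

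**Conclusion.** The point holds as a cheap improvement. Users are admitted, allocation is unstratified, and no analysis in the documents adjusts for their use. A reader might go further and call the primary analysis biased or its alpha inflated. Neither follows, because allocation is random and the simulation shows both properties intact on average.

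What remains is conditional and modest: roughly one trial in eight to ten would have an imbalance of 20 points or more, and the resulting shift is under half a standard error at 20 points. The gain in power is at most about 3.5 percentage points. These sizes rest on the assumed 30% to 50% use and 0.05 to 0.15 L effect, on the plan's SD of 0.25 L, and on 26 evaluable per arm. With a smaller effect or few users, the benefit approaches zero. The sample size of 58 does not change.

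**What to change.** In Section 10.2, prespecify antifibrotic use at randomization (pirfenidone or nintedanib, yes/no) and its interaction with visit as terms in the primary MMRM. State in advance what will be done if there are too few users to estimate them.

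Record baseline use with one yes/no eCRF item at Visit 1 or 2. Report antifibrotic starts after randomization by arm, but do not use them as covariates: in an unblinded trial they may depend on the assigned arm, so they are an intercurrent event and not a chance imbalance.

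The cost is one parameter per visit (five if baseline FVC stays in the response, four if only post-baseline visits are modelled) and one data item. Allocation and enrolment are unaffected.
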